Appendix C. Pregnancy and Lactation Notification Worksheets

Fax Completed Form to the Country-respective Safety Fax Line

SELECT OR TYPE IN A FAX#

1. Case Administrative Information

Protocol/Study Number: _____

Study Design: Interventional Observational (If Observational: Prospective Retrospective)

2. Contact Information

Investigator Name _____ Site # _____

Phone (____) _____ Fax (____) _____ Email _____

Institution _____

Address _____

3. Subject Information

Subject ID # _____ Subject Gender: Female Male Subject DOB: mm____ / dd____ / yyyy____

4. Amgen Product Exposure

Amgen Product	Dose at time of conception	Frequency	Route	Start Date
				mm /dd /yyyy____

Was the Amgen product (or study drug) discontinued? Yes No

If yes, provide product (or study drug) stop date: mm ____/dd____/yyyy____

Did the subject withdraw from the study? Yes No

5. Pregnancy Information

Pregnant female's LMP mm ____ / dd ____ / yyyy____ Unknown

Estimated date of delivery mm____ / dd____ / yyyy____ Unknown N/A

If N/A, date of termination (actual or planned) mm____ / dd____ / yyyy____

Has the pregnant female already delivered? Yes No Unknown N/A

If yes, provide date of delivery: mm ____ / dd____ / yyyy____

Was the infant healthy? Yes No Unknown N/A

If any Adverse Event was experienced by the infant, provide brief details: _____

Form Completed by:

Print Name: _____ Title: _____

Signature: _____ Date: _____

AMGEN[®] Lactation Notification Worksheet

Fax Completed Form to the Country-respective Safety Fax Line

SELECT OR TYPE IN A FAX#

1. Case Administrative Information

Protocol/Study Number: _____

Study Design: Interventional Observational (If Observational: Prospective Retrospective)

2. Contact Information

Investigator Name _____ Site # _____

Phone (____) _____ Fax (____) _____ Email _____

Institution _____

Address _____

3. Subject Information

Subject ID # _____ Subject Date of Birth: mm ____ / dd ____ / yyyy ____

4. Amgen Product Exposure

Amgen Product	Dose at time of breast feeding	Frequency	Route	Start Date
				mm ____ / dd ____ / yyyy ____

Was the Amgen product (or study drug) discontinued? Yes No

If yes, provide product (or study drug) stop date: mm ____ / dd ____ / yyyy ____

Did the subject withdraw from the study? Yes No

5. Breast Feeding Information

Did the mother breastfeed or provide the infant with pumped breast milk while actively taking an Amgen product? Yes No

If No, provide stop date: mm ____ / dd ____ / yyyy ____

Infant date of birth: mm ____ / dd ____ / yyyy ____

Infant gender: Female Male

Is the infant healthy? Yes No Unknown N/A

If any Adverse Event was experienced by the mother or the infant, provide brief details: _____

Form Completed by:

Print Name: _____ Title: _____

Signature: _____ Date: _____

Amendment 2

Protocol Title: A Multicenter, Randomized, Double-blind, Placebo-controlled, Study to Compare the Efficacy and Safety of Romosozumab With Placebo in Postmenopausal South Korean Women With Osteoporosis

Amgen Protocol Number Romosozumab (AMG 785) 20150242

Amendment Date: 13 November 2017

Rationale:

This study is being conducted to support registration of romosozumab in Korea.

A primary analysis at 6 months is being added in this protocol amendment. Conducting a primary analysis in addition to a final analysis allows evaluation of the efficacy and safety data in the most expedited manner to support registrational activities.

Importantly, the primary analysis is being added to maintain consistency with what was done in previous studies with a similar design in the romosozumab development program.

Additional updates include:

- Align End of Study and Publication Policy language to new template text
- Update schema to include primary and final analysis, and add month 5 visit to align with protocol
- Clarify adverse events of interest to include injection site reactions and potential events of serious cardiovascular adverse events
- Make editorial and administrative edits

Description of Changes:

[Section: Global](#)

Change: Date updated throughout from 09 June 2017 to **13 November 2017**.

[figure not shown]
[Section: Title Page](#)

Add:

[figure not shown]
Amendment 02 Date 13 November 2017

[Section: Study Design and Treatment Schema](#)

Replace:

With:

Section: Study Glossary

Add:

EOI	Event of Interest
------------	--------------------------

Section: 3.5.2 End of Study paragraph 1

Add:

The primary completion date is defined as the date when the last subject is assessed or receives an intervention for the final collection of data for the primary endpoint(s), for the purpose of conducting the primary analysis, whether the study concluded as planned in the protocol or was terminated early.

Section: 3.5.2 End of Study paragraph 4

Add:

If the study concludes prior to the primary completion date originally planned in the protocol (ie, early termination of the study), then the primary completion will be the date when the last subject is assessed or receives an intervention for evaluation in the study (ie, last subject last visit).

[Section: 7.3.11 Adverse Events, Serious Adverse Events, and Adverse Device Effects](#)

Replace:

- potential osteonecrosis of the jaw events
- potential cases of atypical femoral fracture

With:

- potential osteonecrosis of the jaw events
- potential atypical femoral fracture **events**
- **injection site reactions**
- **potential events of serious cardiovascular adverse events**

[Section: 10.4.1 Interim Analysis](#)

Add:

10.4.1 Interim Analysis

No interim analyses or sample size re-estimation are planned for this study.

[Section: 10.4.2 Primary Analysis](#)

Add:

10.4.2 Primary Analysis

The primary analysis will be performed after all subjects have had the opportunity to complete the month 6 visit.

The primary objective of the primary analysis is to evaluate the effect of treatment with romosozumab for 6 months compared with placebo on percent changes in BMD at the lumbar spine as assessed by DXA in South Korean women with osteoporosis. Formal statistical testing will be conducted to evaluate the following hypothesis: in South Korean women with osteoporosis, the mean percent change in lumbar spine BMD in subjects receiving romosozumab will be different to that of those receiving placebo at month 6.

Secondary objectives of the primary analysis include the evaluation of the effect of treatment with romosozumab compared with placebo on the following:

- **Percent change from baseline in DXA BMD at the femoral neck and total hip at month 6**

Exploratory objectives of the primary analysis includes the evaluation of the effect of treatment with romosozumab for 6 months compared with placebo on the following:

- Percent changes from baseline in BTMs P1NP and CTX

For the exploratory objectives, all inferential statistics will be considered exploratory in nature.

Safety objectives of the primary analysis include the comparison of the safety and tolerability for 6-month treatment with 210 mg romosozumab QM to placebo in South Korean women with osteoporosis on the following:

- Subject incidence of adverse events, including Event of Interest (EOI)
- Changes from baseline in laboratory assessments (serum chemistry and hematology) and shifts from baseline to the worst value
- Changes from baseline in vital signs
- Incidence of subjects with anti-romosozumab antibodies

[Section: 10.4.3 Final Analysis](#)

Replace:

10.4.1 Final Analysis

The final analysis will be performed after all subjects have had the opportunity to complete the month 9 visit (ie, after all subjects have had the opportunity to complete the 3-month follow-up period). The 3-month follow-up period will provide the opportunity to monitor all subjects for adverse events and formation of anti-romosozumab antibodies.

The primary objective of the additional 3 months is the safety objective (ie the comparison of the safety and tolerability following 6 -month treatment with 210 mg romosozumab QM to placebo in postmenopausal women with osteoporosis)

With:

10.4.3 Final Analysis

The final analysis will be performed after all subjects have had the opportunity to complete the month 9 visit (ie, after all subjects have had the opportunity to complete the 3-month follow-up **study** period). The 3-month follow-up period will provide the opportunity to monitor all subjects for adverse events and formation of anti-romosozumab antibodies.

Final analysis will include the analysis of primary, secondary, exploratory efficacy endpoints, as well as the safety endpoints through 6-month treatment period and the analysis of safety endpoints (adverse events and formation of anti-romosozumab antibodies) for the 9-month study period.

The primary objective of the **final analysis** is the safety objective (ie, the comparison of the safety and tolerability following 9-month treatment with 210 mg romosozumab QM to placebo in **South Korean** women with osteoporosis).

In the final analysis, data from the overall 9-month study period (6-month treatment period plus 3-month follow-up period) will be analyzed.

[Section: 10.5.5.1 Adverse Events](#)

Add:

For the 6-month treatment period, subject incidence of all treatment-emergent adverse events will be tabulated by system organ class and preferred term. Tables of fatal adverse events, serious adverse events, **events of interest (including positively adjudicated osteonecrosis of the jaw, positively adjudicated atypical femoral fracture, injection site reaction, and positively adjudicated serious cardiovascular adverse events)**, adverse events leading to withdrawal from IP or other protocol-required therapies, and treatment-emergent adverse events will also be provided.

[Section: 12.6 Publication Policy](#)

Replace:

Authorship of any publications resulting from this study will be determined on the basis of the Uniform Requirement for Manuscripts Submitted to Biomedical Journals (International Committee of Medical Journal Editors), which states:

- Authorship credit should be based on (1) substantial contributions to conception and design, acquisition of data, or analysis and interpretation of data; (2) drafting the article or revising it critically for important intellectual content; (3) final approval of the version to be published. Authors should meet conditions 1, 2, and 3.
- When a large, multicenter group has conducted the work, the group should identify the individuals who accept direct responsibility for the manuscript. These individuals should fully meet the criteria for authorship defined above.
- Acquisition of funding, collection of data, or general supervision of the research group, alone, does not justify authorship.
- All persons designated as authors should qualify for authorship, and all those who qualify should be listed.

- Each author should have participated sufficiently in the work to take public responsibility for appropriate portions of the content.

With:

Authorship of any publications resulting from this study will be determined on the basis of the Uniform Requirement for Manuscripts Submitted to Biomedical Journals (International Committee of Medical Journal Editors), which states:

- Authorship credit should be based on (1) substantial contributions to conception and design, acquisition of data, or analysis and interpretation of data; (2) drafting the article or revising it critically for important intellectual content; (3) final approval of the version to be published, **and (4) agreement to be accountable for all aspects of the work in ensuring that questions related to the accuracy or integrity of any part of the work are appropriately investigated and resolved.** Authors **need to** meet conditions 1, 2, 3, **and 4.**
- When a large, multicenter group has conducted the work, the group **is to** identify the individuals who accept direct responsibility for the manuscript. These individuals **must** fully meet the criteria for authorship defined above.
- Acquisition of funding, collection of data, or general supervision of the research group, alone, does not justify authorship.
- All persons designated as authors should qualify for authorship, and all those who qualify **are to** be listed.
- Each author **must** have participated sufficiently in the work to take public responsibility for appropriate portions of the content.

Amendment 1

Protocol Title: A Multicenter, Randomized, Double-blind, Placebo-controlled, Study to Compare the Efficacy and Safety of Romosozumab With Placebo in Postmenopausal South Korean Women With Osteoporosis

Romosozumab (AMG 785) 20150242

Amendment Date: 09 June 2017

Rationale:

The protocol is amended to:

- Add independent committee adjudication for deaths and serious adverse events to be of potential cardiovascular origin or etiology
- Revise Hepatitis B and C exclusion criteria to clarify the circumstances under which PCR should be performed to determine active disease
- Add a superscript "a" to CTX and P1NP in Table 2 (Analyte Listing) to indicate that post-day 1 assessments are blinded
- Make minor administrative changes and edits throughout the protocol

12.	Literature Citations / References	25
13.	Appendices	26
13.1	Technical Detail and Supplemental Information Regarding Statistical Procedures and Programs	26
13.1.1	Dates	26
13.1.2	Analysis Visit Windows	26
13.2	Code Fragments	27
13.2.1	Analysis of Covariance (ANCOVA) Model	27
13.2.2	Wilcoxon Rank-sum Test	27
13.2.3	Logistic Regression Model on Binary Response	27

13.2.4	Cox Proportional Hazards Model on Time-to-event Endpoint	28
13.3	Reference Values/Toxicity Grades	28
13.4	Cardiovascular Medical History Risk Factor Preferred Terms.....	29

List of Tables

Table 1.	Imputation Rules on Partial Start Date of AE or Concomitant Medication.....	16
----------	--	----

Table of Abbreviations

Abbreviation or Term	Definition/Explanation
AE	Adverse event
AFF	Atypical femoral fracture
ANCOVA	Analysis of covariance
BMD	Bone Mineral density
BMI	Body mass index
BTM	Bone turnover marker
BP	Blood pressure
CI	Confidence interval
CTCAE	Common terminology criteria of adverse events
CTX	Serum Type 1 Collagen C-Telopeptide
DRE	Disease Related Events
DXA	Dual X-ray absorptiometry
eCRF	Electronic case report form
EDC	Electronic data capture
End of Study (end of trial)	Defined as when the last subject is assessed or receives an intervention for evaluation in the study
End of Study (primary completion)	Defined as when the last subject is assessed or receives an intervention for the purposes of final collection of data for the primary endpoint
End of Study for Individual Subject	Defined as the last day that protocol-specified procedures are conducted for an individual subject
End of Treatment	Defined as the last assessment for the protocol-specified treatment phase of the study for an individual subject
EOS	End of study
FAS	Full analysis set
GCP	Good clinical practice
IP	Investigational Product
IPD	Important protocol deviation
iPTH	Intact parathyroid hormone
IVRS	Interactive voice response system
LLOQ	Lower limit of qualification
MedDRA	Medical dictionary for regulatory activities
MACE	Major Adverse Cardiac Events
ONJ	Osteonecrosis of the jaw
P1NP	Procollagen type 1 N-terminal peptide
PFS	Prefilled syringe

Abbreviation or Term	Definition/Explanation
PMO	Postmenopausal osteoporosis
QM	Every month
Romosozumab	International nonproprietary name for AMG 785
SAP	Statistical analysis plan
SC	Subcutaneous
SD	Standard deviation
SMQ	Standardized MedDRA query
ULOQ	Upper limit of qualification
WHO	World Health Organization

1. Introduction

The purpose of this statistical analysis plan (SAP) is to provide details of the statistical analyses that have been outlined within the protocol for romosozumab Study 20150242 **Amendment 2 dated 13 November 2017**. The scope of this plan includes all analyses that are planned and will be executed by the Biostatistics department or designee unless otherwise specified eg, standard PK tables may be provided by the Clinical Pharmacology, and Modeling and Simulation Group.

2. Objectives

2.1 Primary

To evaluate the effect of treatment with romosozumab for 6 months compared with placebo on percent changes from baseline in bone mineral density (BMD) at the lumbar spine as assessed by dual-energy x-ray absorptiometry (DXA) in postmenopausal women with osteoporosis.

2.2 Secondary

To evaluate the effect of treatment with romosozumab for 6 months compared with placebo on the percent changes from baseline in DXA BMD at the total hip and femoral neck.

2.3 Exploratory

To evaluate the effect of treatment with romosozumab for 6 months compared with placebo on percent changes from baseline in bone turnover markers (BTM): bone formation marker procollagen type 1 N-telopeptide (P1NP) and bone resorption marker serum type I collagen C-telopeptide (CTX).

2.4 Safety

To characterize the safety and tolerability of treatment with romosozumab for 6 months compared with placebo as determined by a review of reported adverse events (AE), laboratory data, vital signs, and the formation of anti-romosozumab antibodies over the 6-month treatment period, and adverse events and the formation of anti-romosozumab antibodies for the overall study period (6-month treatment period followed by the 3-month follow-up period).

2.5 Pharmacokinetics (PK)

To characterize the serum romosozumab concentration at selected time points.

3. Study Overview

3.1 Study Design

This is a multicenter, randomized, double-blind, placebo-controlled study in approximately 60 South Korean postmenopausal women with osteoporosis. The study is designed to evaluate if treatment with romosozumab once a month (QM) for 6 months compared with placebo is effective in increasing BMD at the lumbar spine. In addition, the study will assess the effect of treatment with romosozumab QM for 6 months compared with placebo on BMD at the total hip and femoral neck.

Approximately 60 subjects will be randomized in a 1:1 ratio to receive 210 mg romosozumab subcutaneous (SC) QM (approximately 30 subjects) or matched placebo SC QM (approximately 30 subjects), respectively, in a blinded fashion for the duration of the 6-month treatment period. Upon completion of the 6-month treatment period, subjects will be followed for an additional 3 months to ensure appropriate follow-up for assessing anti-romosozumab antibody formation and safety.

From screening to end of study (EOS), subjects will receive daily calcium and vitamin D supplementation, which at a minimum should be in the range of 500 to 1000 mg elemental calcium and 600 to 800 IU vitamin D. In addition, subjects with a serum 25 (OH) vitamin D level of ≥ 20 ng/mL and ≤ 40 ng/mL at screening will receive an initial loading dose of 50 000 to 60 000 IU vitamin D after randomization (administered within 1 week of the study day 1 visit), preferably by the oral route. Subjects with a serum 25 (OH) vitamin D level of > 40 ng/mL at screening may also receive the vitamin D loading dose at the principal investigator's discretion.

The primary analysis of the study will be performed after all subjects have had the opportunity to complete the Month 6 visit. The final analysis will be performed after all subjects have had the opportunity to complete the Month 9 end of study visit. The overall study design is described by a study schema at the end of the protocol synopsis section.

3.2 Sample Size

The sample size is based on comparison of romosozumab to placebo on percent change from baseline in lumbar spine BMD at month 6. From an earlier Study 20060326, the estimated mean percentage differences in lumbar spine BMD between romosozumab versus placebo at month 6 were 7.9 with 95% CI (6.6, 9.3). The standard deviations (romosozumab vs. placebo) of mean percentage change in lumbar spine BMD at month 6 were 3.9 vs. 3.8. A sample size of 30 subjects per treatment arm will

provide >99% power to detect significant treatment difference (romosozumab vs. placebo) in percent change in lumbar spine BMD at month 6 assuming a mean percent difference of 6.6 and a standard deviation of 3.9 with two-sided type 1 error of 5% and 10% dropout rate under the two sample t-test.

4. Study Endpoints and Covariates

4.1 Study Endpoints

4.1.1 Primary Endpoint

- Percent change from baseline in DXA BMD at the lumbar spine at Month 6

4.1.2 Secondary Endpoints

- Percent change from baseline in DXA BMD at the total hip and femoral neck at Month 6

4.1.3 Exploratory Endpoints

- Percent changes from baseline in BTM: CTX and P1NP at Months 1, 3, and 6

4.1.4 Safety Endpoints

For the 6-month treatment period:

- Subject incidence of AEs by system organ class and preferred term
- Changes from baseline in laboratory assessments (serum chemistry and hematology) and shifts from baseline to the worst value between baseline and Month 6
- Changes from baseline in vital signs
- Incidence of subjects with anti-romosozumab antibodies at Months 1, 3, and 6
- **Subject incidence of adjudicated positive cardiovascular serious adverse events**

For the overall study period (6-month treatment period followed by the 3-month follow up period):

- Subject incidence of AEs by system organ class and preferred term
- Subject incidence of the formation of anti-romosozumab antibodies
- **Subject incidence of adjudicated positive cardiovascular serious adverse events**

4.1.5 Pharmacokinetic Endpoint

- Romosozumab serum concentration at Months 1, 3, and 6

4.2 Planned Covariates

All analyses assessing BMD endpoints at the lumbar spine, femoral neck, and total hip will include treatment, baseline DXA BMD value, machine type (Hologic or Lunar), and the machine type-by-baseline DXA BMD value interaction as independent variables.

5. Hypotheses

The primary clinical hypothesis is that in South Korean postmenopausal women with osteoporosis, the mean percent change from baseline in lumbar spine BMD in subjects receiving romosozumab will be superior to that of those receiving placebo at month 6. It is hypothesized that the mean percent change from baseline in BMD at the lumbar spine in subjects receiving romosozumab will be at least 6.6% greater than that in subjects receiving placebo.

The safety hypothesis is that romosozumab treatment for 6 months is well tolerated in South Korean women with osteoporosis.

6. Definitions

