2.5 Clinical Hypotheses

The primary clinical hypothesis is that in South Korean postmenopausal women with osteoporosis, the mean percent change in lumbar spine BMD at month 6 in subjects receiving romosozumab will be superior to that of those receiving placebo. It is hypothesized that changes in BMD at the lumbar spine in subjects receiving romosozumab will be at least 6.6% greater than in subjects receiving placebo.

The safety hypothesis is that romosozumab treatment for 6 months is well tolerated in South Korean women with osteoporosis.

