10.4.2 Primary Analysis

The primary analysis will be performed after all subjects have had the opportunity to complete the month 6 visit.

The primary objective of the primary analysis is to evaluate the effect of treatment with romosozumab for 6 months compared with placebo on percent changes in BMD at the lumbar spine as assessed by DXA in South Korean women with osteoporosis. Formal statistical testing will be conducted to evaluate the following hypothesis: in South Korean women with osteoporosis, the mean percent change in lumbar spine BMD in subjects receiving romosozumab will be different to that of those receiving placebo at month 6.

Secondary objectives of the primary analysis include the evaluation of the effect of treatment with romosozumab compared with placebo on the following:

- Percent change from baseline in DXA BMD at the femoral neck and total hip at month 6

Exploratory objectives of the primary analysis include the evaluation of the effect of treatment with romosozumab for 6 months compared with placebo on the following:

- Percent changes from baseline in BTMs P1NP and CTX

For the exploratory objectives, all inferential statistics will be considered exploratory in nature.

Safety objectives of the primary analysis include the comparison of the safety and tolerability for 6-month treatment with 210 mg romosozumab QM to placebo in South Korean women with osteoporosis on the following:

- Subject incidence of adverse events, including Event of Interest (EOI)
- Changes from baseline in laboratory assessments (serum chemistry and hematology) and shifts from baseline to the worst value
- Changes from baseline in vital signs
- Incidence of subjects with anti-romosozumab antibodies

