10.1 General Principles

The hypotheses will be tested and the romosozumab treatment effects will be estimated using statistical models and summary statistics.

For computation of change from baseline endpoints, baseline will be taken as the observation recorded just prior to first dose of IP. In the case where the protocol specifies multiple baseline measurements to be taken, the mean of the baseline records will be used for analysis.

All efficacy analyses will be performed by randomized treatment, regardless of actual treatment received.

Continuous variables will be summarized descriptively using mean, median, standard deviation, 25th percentile, 75th percentile, minimum, maximum, and the number of non-missing observations. Frequencies and percentages will be presented for nominal categorical variables.

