10.6.1 Primary Analysis of Primary Efficacy Endpoint

The primary analysis to assess the percent change from baseline in lumbar spine DXA BMD at Month 6 will employ an ANCOVA model. The ANCOVA model will include treatment, baseline DXA BMD value as main effects. Additional covariates of machine type (Hologic or Lunar) and machine type by baseline DXA BMD value interaction will also be included in the model to adjust for the effect of machine type on baseline DXA BMD value. SAS procedure PROC MIXED is to be used to obtain the least squares means (LSM) point estimates of the percent change from baseline for each treatment

arm. Model based adjusted treatment difference of LSM with associated 95% CI and corresponding p-value will be presented. SAS code fragments are provided in Appendix 13.2.1.

Conclusion for the primary efficacy hypothesis of different efficacy of romosozumab compared with placebo at lumbar spine BMD at 6 months will be made using a 2 sided test with type 1 error rate of 0.05.

The primary analysis will use the BMD efficacy analysis set.

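### Does hypothesising a gain of at least 6.6 points over placebo require a test against 6.6 rather than against zero?

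*SAP*

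**What the plan says.** The number 6.6 plays two roles.

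- **As a hypothesis.** SAP 5 adds to its superiority statement that the mean change "in subjects receiving romosozumab will be at least 6.6% greater than that in subjects receiving placebo". Protocol 2.5 hypothesises that "changes in BMD at the lumbar spine in subjects receiving romosozumab will be at least 6.6% greater than in subjects receiving placebo", and the synopsis repeats it.
- **As a planning value.** SAP 3.2 and Protocol 10.2 cite an earlier study with a difference of 7.9 (95% CI 6.6 to 9.3). They claim more than 99% power with 30 per arm and 10% dropout, "assuming a mean percent difference of 6.6 and a standard deviation of 3.9". So 6.6 is the lower confidence limit of the earlier estimate, taken as a cautious assumed effect.

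On testing, SAP 10.1 says in general terms: "The hypotheses will be tested and the romosozumab treatment effects will be estimated using statistical models and summary statistics". The specific text is narrower. Protocol 10.4.2 gives the formally tested hypothesis as "the mean percent change in lumbar spine BMD in subjects receiving romosozumab will be different to that of those receiving placebo at month 6". SAP 10.6.1 bases its "Conclusion for the primary efficacy hypothesis of different efficacy of romosozumab compared with placebo at lumbar spine BMD at 6 months" on a two-sided test at the 0.05 level. It also calls for the adjusted treatment difference with its 95% CI. Neither document uses 6.6 as a null value, margin or success criterion.

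**The concern.** Taken literally, the second sentence of the hypothesis is a minimum-effect claim, and SAP 10.1 appears to promise that it will be tested. The planned test can reject zero. It cannot show that the difference is at least 6.6.

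A reader might then credit the power of more than 99% to the stronger claim. A report might call the hypothesis confirmed because p is below 0.05, or because the point estimate happens to exceed 6.6. A clearly positive trial with an estimate below 6.6 might be said to have missed its own hypothesis. Amendment 2 gives support for registration in Korea as the purpose of the study, so what a significant p-value licenses ought to be clear.

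**Working it through.** **Inputs.** 30 per arm, 10% dropout, SD 3.9, two-sided 5% and an assumed difference of 6.6 (SAP 3.2, Protocol 10.2). Earlier estimate 7.9, 95% CI 6.6 to 9.3 (same sections). Evaluable per arm: 30 × 0.90 = 27. The plan bases its power on an unadjusted two-sample t-test, and so does this check.

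**1. The plan's own figure.**
- SE = 3.9 × √(2/27) = 1.061.
- Noncentrality against zero = 6.6 / 1.061 = 6.22, on 52 degrees of freedom.
- Power = 99.998% (noncentral t); with 30 per arm it is 99.9996%.
- By the normal formula, 13 evaluable per arm would already give 99%.

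The stated figure of more than 99% is reproduced, for the test against zero.

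**2. What the planned interval can show.**
- 95% half-width = 2.007 × 1.061 = 2.13.
- Observed difference needed to exclude zero: above 2.13.
- Observed difference needed to exclude 6.6: above 6.6 + 2.13 = 8.73.

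**3. Chance that the lower limit exceeds 6.6.** The noncentrality is (true difference − 6.6) / 1.061.

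| True difference | Source | Noncentrality | Probability (27 per arm) |
|---|---|---|---|
| 6.6 | planning value, lower limit | 0 | 2.5% |
| 7.9 | earlier estimate | 1.22 | 22.4% |
| 9.3 | upper limit | 2.54 | 70.4% |

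With 30 per arm and a true difference of 7.9 it is 24.5%. For 90% power at 7.9, n per arm = 2 × (1.960 + 1.282)² × (3.9/1.3)² ≈ 190 evaluable, or 190/0.9 ≈ 212 randomised.

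**4. The awkward case, an estimate of 6.0.** The interval is 6.0 ± 2.13, or 3.87 to 8.13. It excludes zero, so the primary conclusion in SAP 10.6.1 and Protocol 10.5.2 is reached. Falling short of 6.6 triggers nothing, because no rule refers to 6.6.

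**5. How far the general sentence in SAP 10.1 reaches.** It cannot mean that every statement in SAP 5 receives a test. SAP 5 also hypothesises that treatment is well tolerated, and Protocol 10.5.5 rules out inferential testing of safety. The sentence introduces the methods; Protocol 10.4.2 and 10.5.2 and SAP 10.6.1 define the test. The Protocol has no equivalent general sentence.

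**The case for a change.** The strongest case for a change is that the sentence stands under a heading for hypotheses, in a SAP that says the hypotheses will be tested. For an observed difference between about 2.1 and 8.7, a reader who knew only SAP 5 could argue over whether the hypothesis was met. A point estimate above 6.6 would settle nothing: with a true difference of 6.0 it would occur in about 29% of trials (0.6 / 1.061 = 0.57 standard errors). The remedy would be one sentence in three places.

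Part of this stands. A planning value has been restated as a minimum effect, and the design could not reliably support such a claim. The rest does not. Both documents state the tested hypothesis and the decision rule, so the ambiguity disappears once SAP 10.6.1 or Protocol 10.4.2 is read. Neither document attaches the power to a 6.6 threshold; both attach it to detecting a significant difference when 6.6 is assumed true. The feared misreadings would be reporting errors that the plan does not authorise, and the planned interval would expose them. Nor is the edit free on the protocol side: under Protocol 11.2 and 12.1 an amendment needs investigator agreement and ethics committee approval.

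**Conclusion.** No change follows. The 6.6 sentence is a loosely worded statement of expected effect. The trial's formal question is whether the difference is zero, and that question is correctly powered and has a clear decision rule. An analyst who follows the SAP exactly reaches a sound primary conclusion and reports the interval from which magnitude can be judged, including against 6.6. Deleting or relabelling the sentence would alter no sample size, model, estimate, p-value or decision.

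The probabilities of 2.5%, 22% and 70% describe how seldom or often this trial's interval would exclude 6.6 if the truth were 6.6, 7.9 or 9.3. They rest on 27 evaluable per arm, SD 3.9 and an unadjusted t-test. The planned ANCOVA could reduce the residual SD and raise the last two; the documents give no figure for that. None of the three is the power of an analysis in the plan.
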